7.6 Missing data

Sensitivity analyses will be undertaken to assess the impact of missing data for the primary outcome, by imputing extreme values of change within treatment arm (i.e. smallest and largest change from the previous time point to 24 months). Results between the atropine and placebo groups will be compared using GEE and 95% CIs and will be adjusted for baseline SER and also adjusted for baseline SER, minimisation variables (i.e site and ethnicity), baseline age and history of parental myopia (at least one parent). If the baseline primary outcome is missing, spectacle refraction based on the current prescription at baseline will be used in the sensitivity analysis.

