3.4 Data verification

Data verification, consistency and range checks will have been performed at the data entry stage by the CTU, as well as checks for missing data (copies can be found in the TMF) according to SOP DM04. Additional range, consistency and missing data checks will be performed, as appropriate, when the analysis is performed (and when the datasets for analysis are constructed). All variables will be examined for unusual, outlying, unlabelled or inconsistent values.

Given the thorough nature of our follow-up procedure we expect the issue of missing data to be relatively minimal. We anticipate high compliance with initial data collection as this is close to the time of patient registration.

If any clinical data is missing for the primary outcome at 24 months, imputation will be carried out by imputing extreme values of change within treatment arm (i.e. smallest and largest change from the previous time point to 24 months) in a sensitivity analysis. If the baseline primary outcome is missing, spectacle refraction will be used in the sensitivity analysis.

Study drug adherence will be self-reported and the event logs will be extracted from the MEMS during visits via a device connected to the computer to assess study drug adherence.

Any problems with trial data will be queried with the Trial Managers, Data Managers, or statisticians, as appropriate. If possible, data queries will be resolved, although it is accepted that due to administrative reasons and data availability a small number of problems will continue to exist. This will be minimised.

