5. SAMPLE SIZE CALCULATIONS

We anticipate that the effect of atropine eye drops in a UK population will be smaller than the reported effect in Chinese populations, but assuming that atropine reduces the progression of myopia by at least 40% in 24 months from a control mean of -0.8D7 (40% of 0.8 is equivalent to a mean difference of -0.32D between intervention and control group at 24 months), using SD=0.7D, a correlation (interclass correlation coefficient) between eyes of 0.9 and a variation inflation factor of 1.9, we will need 97 participants in each group. Considering a dropout rate of 15% and that 10% of the recruited children will be Chinese, we will need a total of 289 participants: 193 atropine, 96 placebo (152 atropine, 76 placebo inflated by a variance inflation factor of 1.9) to detect this difference in the non-Chinese population with 90% power.

Justification: In a study of 400 Chinese children evaluating the effect of 24 months of 1% atropine eye drops, myopia progression was -1.20 +/- 0.69 D in the placebo control group, and -0.28 +/- 0.92 D in the atropine group. We have assumed that progression of myopia and efficacy of atropine will be less in UK children than in Chinese children2.

Progression of myopia of untreated children was estimated from the control groups of randomized controlled trials for myopia. The following progression data have been reported:

- Katz 2003⁴ (Chinese race): progression of -1.28D (SD 0.78) D after 2 years (control was spectacles)
- Edwards 2002⁵ (Chinese race): progression of -1.26D (SD 0.74) D after 2 years (control was single vision lenses)
- Chua 2006³, ATOM study (Chinese race): progression of -1.20D (SD 0.69) after 2 years (control was placebo drops)
- Hyman 2005⁶, COMET trial (children of mixed races, with whites being the most common ethnicity): progression of 1.32D after 3 years (standard error 0.04) (control was single vision lenses)
- Breslin 2013⁷, In an observational study from the UK, myopia progression was 1.14D after 3 years.

Doc No: ST06-RD01 Page **12** of **47**

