7.1 Primary outcome

The principal analysis will be based on complete case data without imputation for those who dropped out of the study before the end of the 24 months. The primary outcome (SER at month 24) results from both eyes will be used and adjusted for baseline SER. The atropine and control groups will be compared using generalised estimating equations (GEE) and 95% confidence intervals (CIs), to allow for the correlation between eyes within a participant. Secondary analysis of the primary outcome will be adjusted for baseline SER, minimisation variables (i.e. site and ethnicity), baseline age and history of parental myopia (at least one parent).

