Eye feels f	ITT	$xx.x \pm xx.x n=$	$xx.x \pm xx.x n=$	xx.x (x.x, x.x)	x.xx			
Lye reers	PP	$xx.x \pm xx.x n=$	$xx.x \pm xx.x n=$	xx.x (x.x, x.x)	X.XX			
Stingy ^f	ITT	$xx.x \pm xx.x n=$	$xx.x \pm xx.x n=$	xx.x (x.x, x.x)	X.XX			
Strigy	PP	$xx.x \pm xx.x n=$	$xx.x \pm xx.x n=$	xx.x (x.x, x.x)	X.XX			
Itchiness f	ITT	$xx.x \pm xx.x n=$	$xx.x \pm xx.x n=$	xx.x (x.x, x.x)	X.XX			
1ttilless	PP	$xx.x \pm xx.x n=$	$xx.x \pm xx.x n=$	xx.x (x.x, x.x)	x.xx			
Blurry vision ^f	ITT	$xx.x \pm xx.x n=$	$xx.x \pm xx.x n=$	xx.x (x.x, x.x)	X.XX			
Diuliy Vision	PP	$xx.x \pm xx.x n=$	$xx.x \pm xx.x n=$	xx.x (x.x, x.x)	x.xx			
Sore eyes ^f	ITT	$xx.x \pm xx.x n=$	$xx.x \pm xx.x n=$	xx.x (x.x, x.x)	X.XX			
	PP	xx.x ± xx.x n=	$xx.x \pm xx.x n=$	xx.x (x.x, x.x)	X.XX			
Difficult to	ITT	$xx.x \pm xx.x n=$	$xx.x \pm xx.x n=$	xx.x (x.x, x.x)	X.XX			
read/write f	PP	xx.x ± xx.x n=	$xx.x \pm xx.x n=$	xx.x (x.x, x.x)	X.XX			

^a Adjusted for baseline SER. ^b Adjusted for baseline SER, minimisation variables (i.e. site and ethnicity), age and history of parental myopia (at least one parent). ^c Mean(SD) was calculated with data from both eyes. Mean difference estimate and p value from GEE. ^d Mean difference estimate and p value from ANCOVA. ^e Frequency (%) presented for categorical variables and risk difference and p value from the chi-square test (or fishers exact test if applicable). ^f Mean(SD) and p value from independent samples t-test, no adjustment as tolerability not measured at baseline.

Table XXX: Sensitivity analysis of primary outcome

		Treatme	Treatment Group		ted	Adjuste	ed ^a	Adjus	sted ^b
Primary Outcome		Atropine sulfate N=	Placebo N=	Mean difference (95% CI)	P value	Mean difference (95% CI)	P value	Mean difference (95% CI)	P value
Intention to	treat								
Spherical equivalent refractive	Smallest change	xx.x ± xx.x n=	xx.x ± xx.x n=	xx.x (x.x, x.x)	x.xx	xx.x (x.x, x.x)	x.xx	x.xx	x.xx
error at 24 months ^c	Largest change	xx.x ± xx.x n=	xx.x ± xx.x n=	xx.x (x.x, x.x)	x.xx	xx.x (x.x, x.x)	x.xx	x.xx	x.xx
Per Protocol									
Spherical equivalent	Smallest change	xx.x ± xx.x n=	xx.x ± xx.x n=	xx.x (x.x, x.x)	x.xx	xx.x (x.x, x.x)	x.xx	x.xx	x.xx
refractive error at 24 months ^c	Largest change	xx.x ± xx.x n=	xx.x ± xx.x n=	xx.x (x.x, x.x)	x.xx	xx.x (x.x, x.x)	x.xx	x.xx	x.xx

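### The missing-data sensitivity analysis for month-24 SER moves both arms in the same direction; no opposing or tipping-point scenario is planned

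*Supplement*

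**What the plan says.** SAP section 7.1: "The principal analysis will be based on complete case data without imputation for those who dropped out of the study" before month 24.

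SAP section 7.6 gives the sensitivity analysis for a missing month-24 value: "by imputing extreme values of change within treatment arm (i.e. smallest and largest change from the previous time point to 24 months". Section 3.4 repeats it: "imputation will be carried out by imputing extreme values of change within treatment arm". The only other provision concerns baseline: "If the baseline primary outcome is missing, spectacle refraction based on the current prescription at baseline will be used in the sensitivity analysis".

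Neither section says how the two arms' extremes are to be combined. That comes from the Appendix 1 shell, "Table XXX: Sensitivity analysis of primary outcome". It has one *Smallest change* row and one *Largest change* row, for ITT and again for per protocol. Each row has an atropine column, a placebo column and a single treatment difference. No row crosses the directions, and the SAP contains no delta adjustment, tipping point or multiple imputation.

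Section 5 plans for appreciable loss: "Considering a dropout rate of 15% and that 10% of the recruited children will be Chinese". It does not split the 15% by arm.

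**The concern.** Dropout biases a treatment difference when the missing children of one arm differ from those of the other. The pattern most able to overturn a positive result is missing atropine children progressing more, and missing placebo children less, than those observed. A sensitivity analysis that moves both arms the same way does not test that pattern. If the two planned rows sit close to the complete-case estimate, the report may call the result robust to missing data when the threatening scenario was never run.

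A second gap concerns early leavers. If the previous time point is month 18, a child last seen at month 6 has no value to add the change to. If it is the last attended visit and a single interval's change is added, two of the three remaining intervals are left out.

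**Working it through.** **Inputs from SAP section 5.** "40% of 0.8 is equivalent to a mean difference of -0.32D between intervention and control group at 24 months"; control mean -0.8 D, hence atropine -0.48 D; SD 0.7 D; between-eye correlation 0.9; 193 atropine and 96 placebo; 15% dropout. Below, the effect is atropine minus placebo, so +0.32 D favours atropine.

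**The plan's own figure.** Placebo eyes at 2:1, two-sided 5% (assumed; sidedness is not stated), 90% power: 1.5 × (1.960 + 1.282)² × 0.7² / 0.32² = 75.4, so 76, with 152 atropine eyes. Times 1.9/2: 72.2 and 144.4 children. Divided by 0.75 (15% dropout plus 10% Chinese): 96.3 and 192.5, total 288.8, which is the plan's 289. The inputs are therefore read correctly, and the sample size is not at issue.

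**First-order formula.** Let p be an arm's missing fraction, e its imputed extreme and m its mean 6-month change. Then

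shift in effect = p_A(e_A - m_A) - p_P(e_P - m_P).

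Under linear progression m_A = -0.48/4 = -0.12 D and m_P = -0.8/4 = -0.20 D. With an assumed 6-month SD of 0.3 D, the simulated average extremes are -0.96 and +0.73 D (atropine) and -0.97 and +0.57 D (placebo). At p = 0.15 in both arms:

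- Largest in both: 0.15(-0.84) - 0.15(-0.77) = -0.01 D.
- Smallest in both: 0.15(0.85) - 0.15(0.77) = +0.01 D.
- Atropine largest, placebo smallest: 0.15(-0.84) - 0.15(0.77) = -0.24 D, leaving 0.08 D.
- The reverse: +0.24 D, giving 0.56 D.

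**Simulation.** 193:96 children, two eyes, 1,500 runs per setting, with a Welch test on the child's mean in place of GEE. Assumptions not in the SAP: 6-month SD, independent increments, linear progression, and a month-18 value for every dropout. Smallest change is taken as the least myopic signed change. Cells give the mean effect in D and the share of runs significant for atropine.

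15% missing in both arms:

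| 6-month SD | Complete case | Smallest/smallest | Largest/largest | Atropine largest, placebo smallest | Reverse |
|---|---|---|---|---|---|
| 0.20 | 0.32 (93%) | 0.33 (96%) | 0.31 (94%) | 0.16 (45%) | 0.48 |
| 0.30 | 0.32 (94%) | 0.34 (96%) | 0.31 (93%) | 0.08 (15%) | 0.56 |
| 0.35 | 0.32 (92%) | 0.33 (95%) | 0.30 (88%) | 0.04 (6%) | 0.59 |
| 0.45 | 0.32 (93%) | 0.34 (93%) | 0.30 (87%) | -0.04 (1%) | 0.68 |

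A separate simulation with dropout after any visit and a 6-month SD of about 0.39 D gave 0.316 (complete case), 0.319 (smallest), 0.291 (largest), and 0.00 and 0.61 (opposed).

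Unequal dropout that still averages 15%: (0.20 × 193 + 0.05 × 96)/289 = 15.0% and (0.10 × 193 + 0.25 × 96)/289 = 15.0%.

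| 6-month SD | 20% atropine, 5% placebo: largest/largest | 10% atropine, 25% placebo: smallest/smallest |
|---|---|---|
| 0.20 | 0.233 (76%) | 0.248 (80%) |
| 0.30 | 0.192 (58%) | 0.214 (65%) |
| 0.35 | 0.169 (46%) | 0.192 (53%) |
| 0.45 | 0.125 (25%) | 0.163 (39%) |

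The formula shows why these rows move: p_A and p_P no longer match. Each row still moves the missing children of both arms the same way.

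**If smallest means smallest in absolute size**, about 0 D, the opposed shift at SD 0.3 is 0.15(-0.84) - 0.15(0 + 0.20) = -0.16 D, leaving 0.16 D. The SAP does not say which is meant.

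**Early leavers.** A child last seen at month 6 has three intervals left. A single interval's change omits on average 2 × 0.20 = 0.40 D of placebo progression or 2 × 0.12 = 0.24 D of atropine progression.

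**The case against.** A reader might infer that the plan imputes the same value in both arms, that the shifts always cancel, or that the analysis could never challenge the result. The documents do not support any of these. Section 7.6 takes extremes within treatment arm; only the direction is shared, and only through the shell. Offsetting needs similar dropout proportions, and section 5 gives no split by arm. The second table shows the planned rows can lose significance at 15% overall dropout.

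The opposed result is also an extreme. At SD 0.3 D it makes every missing placebo child about 0.57 D less myopic in six months, in a group assumed to progress 0.8 D over 24 months. That is a bound, not a forecast, and its size depends on an assumed SD.

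The SAP has other partial safeguards. The secondary model adjusts for baseline SER, site, ethnicity, age and parental myopia, which helps if dropout depends on those. The repeated-measures GEE at months 6, 12 and 18 uses children who leave later. Neither tests outcome-dependent missingness at month 24.

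On early leavers, the rule could also be read as the extreme change from the child's own last visit to month 24, which would carry progression forward. The SAP does not say so. In the largest row, one extreme interval may also exceed the average progression omitted.

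What remains is that no scenario lets missing children fare worse in one arm and better in the other.

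**Conclusion.** The concern holds in limited form. The only imputation analysis for missing month-24 SER applies arm-specific extremes in the same direction to both arms. With similar dropout it moves a 0.32 D effect by about 0.01 to 0.03 D. With unequal dropout it moves further, but the movement reflects the imbalance and says nothing about whether missing atropine children fared worse than missing placebo children. The opposed pairing of the same extremes would leave about 0.16 D down to about 0 D (6-month SD 0.2 to 0.4 D, 15% dropout in both arms). The plan would never report that bound.

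These sizes rest on the simulation assumptions above, chiefly the SD. The conclusion that opposing directions add where shared directions subtract follows from the formula alone. The rule for children who leave before month 18 is also unsettled. The primary estimate and test are unaffected, so this is a cheap improvement that should be made, not a fault that invalidates the analysis.

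**What to change.** Amend SAP sections 3.4 and 7.6 and the Appendix 1 shell, before the analyst sees allocation.

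1. As a minimum, add two rows: atropine largest with placebo smallest, and the reverse. Label them as worst-case bounds.
2. Preferably, use delta-adjusted multiple imputation. Impute month-24 SER by arm from SER at all visits and both eyes. Add arm-specific shifts (atropine only, placebo only, both in opposite directions) and report the shift at which the 95% CI includes 0. For the grid: the variance of a child's two-eye mean is 0.49 × (1 + 0.9)/2 = 0.4655. With 85% observed (about 164 and 82), SE = √[0.4655(1/164 + 1/82)] = 0.092, and 0.32 - 1.96 × 0.092 = 0.14. Significance at the design effect is then lost at about 0.14/0.15 = 0.93 D in atropine alone, or about 0.46 D each way. A grid from 0 to 1 D would cover this. Replacing the extreme-value analysis altogether is optional.
3. Define the previous time point, carry early leavers' progression forward to month 24, and say whether change is signed or absolute.

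The cost is SAP wording, a short extra program and a wide bound to interpret. SER is already collected at every visit, so no new data are needed.

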8.6 Sensitivity analyses

- SER at month 24: mean (SD) by treatment arm, difference in means with 95% CI, p-value from GEE model, adjusted for baseline SER in ITT and PP analysis.
- SER at month 24: mean (SD) by treatment arm, difference in means with 95% CI, p-value from GEE model, adjusted for baseline SER and minimisation variables (i.e. site and ethnicity), baseline age and history of parental myopia (at least one parent), in ITT and PP analysis.

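### The missing-data sensitivity table appears to pair the same extreme in both arms, so at similar dropout it hardly moves the treatment difference and never tests different outcomes among dropouts by arm

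*Supplement*

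**What the plan says.** SAP section 7.1: "The principal analysis will be based on complete case data without imputation". Section 3.4 gives the rule for a missing 24-month value as "imputing extreme values of change within treatment arm (i.e. smallest and largest change from the previous time point to 24 months". Section 7.6 repeats it, again as "imputing extreme values of change within treatment arm", and states its purpose, which is to assess the effect of missing primary-outcome data. Neither section says which extreme in one arm goes with which extreme in the other, or whether smallest and largest refer to signed or absolute change.

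Section 8.6 names no scenarios. It lists outputs only, of the form "SER at month 24: mean (SD) by treatment arm, difference in means with 95% CI, p-value from GEE model, adjusted for baseline SER in ITT", with a covariate-adjusted counterpart. The scenarios appear only in Appendix 1, in "Table XXX: Sensitivity analysis of primary outcome". For each population that table has one "Smallest change" row and one "Largest change" row, and each row holds both arms and a single mean difference per model. There is no row with opposite extremes.

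The SAP describes no multiple imputation, delta adjustment or tipping-point analysis. Substituting spectacle refraction (section 7.6) deals with a missing baseline. The repeated-measures GEE of section 7.5 reports months 6, 12 and 18 and is not presented as a missing-data analysis.

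**The concern.** The quantity under test is a difference between arms. Missing children can overturn it if those lost from atropine fared differently from those lost from placebo, for example if atropine dropouts progressed more. A table that moves the missing children of both arms in the same direction leaves that scenario out. Imputing extremes reads like a bounding exercise, yet these two rows do not bound the treatment effect. If a stable estimate across them were reported as robustness to dropout, the statement would rest on scenarios that could hardly have moved it when dropout is similar by arm.

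**Working it through.** **Inputs from SAP section 5:** 193 atropine and 96 placebo children, difference 0.32 D, SD 0.7 D, between-eye correlation 0.9, variance inflation factor 1.9, dropout 15% (one rate, not split by arm), power 90%. Section 7 gives alpha 0.05, taken as two-sided.

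**Assumptions not in the SAP:** SD of the 18-to-24-month change 0.2, 0.3 or 0.4 D; a quarter of the 24-month change falls in those six months; every dropout has a month-18 value; the by-arm dropout splits below.

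**The plan's own figure.** Placebo eyes: (1 + 1/2) × (1.960 + 1.282)² × 0.7² / 0.32² = 75.4, so 76, with 152 atropine eyes. Participants: 228 × 1.9 / 2 = 216.6. Then 216.6 / (1 − 0.15 − 0.10) = 288.8, so 289 as stated.

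**Complete-case precision.** At 15% dropout 164 and 82 children remain. SD of the two-eye mean: 0.7 × √((1 + 0.9)/2) = 0.682. SE: 0.682 × √(1/164 + 1/82) = 0.092 D, so z is about 0.32 / 0.092 = 3.5.

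**Why the rows nearly cancel.** Let f be an arm's missing fraction and d the distance from its mean 6-month change to its own extreme. Differences are atropine minus placebo, positive meaning less myopia on atropine.

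- Both smallest: the difference moves by +f(A)d(A) − f(P)d(P).
- Both largest: by −f(A)d(A) + f(P)d(P).
- Atropine largest with placebo smallest: by −[f(A)d(A) + f(P)d(P)].

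**Simulation at 15% in each arm** (3,000 trials per setting, two eyes per child, each arm's own observed extreme imputed, z test on child means in place of GEE). Mean difference in D, with the share of trials significant for atropine:

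| Row | SD 0.2 | SD 0.3 | SD 0.4 |
|---|---|---|---|
| Complete case | 0.321 (94%) | 0.319 (93%) | 0.319 (93%) |
| Both smallest | 0.329 (96%) | 0.333 (96%) | 0.337 (95%) |
| Both largest | 0.309 (94%) | 0.304 (92%) | 0.299 (89%) |
| Atropine largest, placebo smallest | 0.159 (44%) | 0.078 (14%) | −0.003 (2%) |
| Atropine smallest, placebo largest | 0.479 (100%) | 0.558 (100%) | 0.638 (100%) |

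At SD 0.3, taking each arm's two extremes as equally distant, f(A)d(A) − f(P)d(P) = 0.333 − 0.319 = 0.014 and f(A)d(A) + f(P)d(P) = 0.558 − 0.319 = 0.239. The arm shifts are therefore (0.239 + 0.014)/2 = 0.13 D for atropine and (0.239 − 0.014)/2 = 0.11 D for placebo. Subtracted, they leave about 0.01 D; added, 0.24 D.

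A differently built simulation (child-specific slopes, ANCOVA on baseline with robust SE, SD of 6-month change 0.25 to 0.35 D) gave 0.33 to 0.34 D for both smallest, 0.30 to 0.31 D for both largest, and 0.04 to 0.12 D for the adverse crossed row.

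**Unequal dropout** (atropine/placebo; SD 0.2 / 0.3 / 0.4):

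| Dropout | Both smallest | Both largest | Atropine largest, placebo smallest |
|---|---|---|---|
| 20% / 10% | 0.37 / 0.41 / 0.44 | 0.26 / 0.23 / 0.21 | 0.15 / 0.07 / −0.01 |
| 20% / 5% | 0.41 / 0.45 / 0.49 | 0.23 / 0.19 / 0.15 | 0.18 / 0.11 / 0.04 |
| 10% / 20% | 0.28 / 0.25 / 0.23 | 0.37 / 0.39 / 0.41 | 0.16 / 0.09 / 0.01 |

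At 20%/5% the both-largest row is significant in 78%, 56% and 37% of trials. In every setting the adverse crossed row lies below both planned rows.

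**If smallest means absolute change.** The imputed value is then close to zero. The last-six-month means are 0.25 × 0.48 = 0.12 D (atropine, from 0.80 − 0.32) and 0.25 × 0.80 = 0.20 D (placebo). At 15% in each arm the difference moves by 0.15 × (0.20 − 0.12) = 0.012 D, again very little.

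**The case against.** A reader might infer that the planned analysis cannot show dropout overturning the result, or that it will come out stable almost whatever happens. The SAP does not support that. Near-cancellation needs similar missing fractions in the two arms, and section 5 gives one overall 15% without saying that it applies equally by arm. At 20%/5% the both-largest row falls to 0.15 to 0.23 D and often loses significance. All runs also fix the true difference at 0.32 D; with a weaker or borderline effect, a shift of 0.01 to 0.02 D could change significance.

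The pairing is also inferred. Sections 3.4 and 7.6 do not state it, and the same-direction reading rests on two row labels in a blank table. It is the natural reading, and the table has no place for any other pairing.

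Three further points stand. The size of the crossed shifts depends on an SD that the SAP does not give. The SAP sets no robustness criterion and promises no such claim. Crossed extremes are severe, since every missing child receives the single most extreme change seen in that arm. Section 3.4 expects few missing data, although section 5 allows for 15%.

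These points limit the strength of the criticism. They do not supply the missing scenario: when dropout is unequal, the planned rows move because the rates differ, and still apply the same direction in both arms.

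**Conclusion.** The point holds in a limited form. As the table is laid out, and if dropout is similar by arm, the sensitivity analysis moves a 0.32 D difference by about 0.01 to 0.02 D, against about 0.16 to 0.32 D for opposite extremes. If dropout is clearly unequal the planned rows can move a good deal, but they neither examine different outcomes among dropouts in the two arms nor show the worst case. The contrast holds across the assumed SD range of 0.2 to 0.4 D; the exact sizes depend on that SD and on all dropouts having a month-18 value. The primary estimate and its test are unaffected. This should be fixed because it is cheap and improves what can be said about dropout; it is not a fault that undermines the trial.

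**What to change.** In sections 7.6 and 8.6 and in the Appendix 1 table:

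- State how the extremes are paired across arms, and whether smallest and largest are signed or absolute changes.
- Add two rows per population: atropine largest with placebo smallest, and the reverse.
- Alongside these or instead, add a by-arm delta-adjusted analysis: multiply impute 24-month SER, shift the imputed atropine values towards more myopia in fixed steps (0.1 D, say) and, separately, the placebo values towards less, and report the delta at which the 95% CI first includes zero.
- Say that any statement about robustness to dropout will rest on these differential scenarios, not on the same-direction rows alone.

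The cost is some SAP wording, two table rows per population and a short program, with no new data. The crossed rows are pessimistic by design, so they should be read as bounds alongside the delta analysis.
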